#### Exploratory Endpoints

- *Time to deterioration of QoL:* Defined as time from randomization to a 10-point reduction of the FACT-P total score.
- *Time to pain progression:* Defined as time from randomization to an increase of 30% in pain severity score from baseline using the BPI-SF.

Time to event endpoints such as rPFS, time to PSA progression, time to first SSE, time to castration resistance, time to deterioration of QoL, time to pain progression and time to initiation of new antineoplastic therapy will be analyzed using the stratified log-rank test. The stratified Cox Regression analysis, with just treatment effect as a factor in the model, will be used to estimate the HR and the associated 95% CI. The median will be estimated using the Kaplan-Meier method.

The proportion endpoints such as PSA Response  $\geq 50\%$ , PSA Response  $\geq 90\%$ , PSA undetectable rate and ORR will be analyzed using the stratified Cochran-Mantel-Haenszel score test.

#### **Safety:**

Frequency and severity of adverse events, safety laboratory tests, physical examinations, ECG and vital signs will be summarized descriptively.

[figure not shown]
#### **Interim Analysis:**

An interim analysis is planned to occur after approximately 60 PSA progression events (about 80% of the total planned events) are observed. TPP will be tested for efficacy according to the O'Brien-Fleming boundary as implemented by Lan-DeMets alpha spending function. Data cut-off dates will be set when the planned number of events is reached for the interim and final analyses. If the exact number of events at interim and final analyses are different than planned, the significance level will be adjusted accordingly, based on the O'Brien-Fleming method with a Lan-DeMets alpha spending function. The IDMC may recommend to the sponsor whether the trial should be terminated or continue unchanged based on interim analysis.

- CONFIDENTIAL -

## V. FLOW CHART AND SCHEDULE OF ASSESSMENTS

### Flow Chart

LHRH: luteinizing hormone-releasing hormone; PSA: prostate-specific antigen.

a. For those subjects who discontinue study treatment without radiographic disease progression confirmed, radiographic assessments will continue every 12 weeks until confirmed radiographic progression by investigator assessment or the required number of PSA progression events for the final analysis is reached.

b. Before the sponsor's formal determination on study-wide unblinding, open-label enzalutamide will be supplied for free to the subjects in placebo arm who remain on study treatment until confirmed radiographic disease progression and in the judgement of the investigator who is necessary to initiate the next course of therapy till next disease progression based on subject's informed consent. If the study results in a positive outcome and after the sponsor's formal determination on study-wide unblinding via written notice to study sites, open-label enzalutamide will be supplied for free to the subjects in both enzalutamide and placebo arms who remain on study treatment (See [Appendix 12.10] for the flow chart and detailed information).

- CONFIDENTIAL -

**Table 1 Schedule of Assessments**

Study Day	Screening Visit ¶¶¶	1 #	29	57	85 and Every Subsequent 28 Days	Safety Follow-up	Unscheduled Visit †	Long Term Follow-up ‡	
								Post Treatment Follow-up	Survival Follow-up
Study Week	-4 to -1 (28 Days)	1	5	9	13 and Every Subsequent 4 Weeks	30 Days after Last Dose §	Every 12 Weeks	Every 12 Weeks	
Window (Days)			± 3	± 3	± 3	± 7	NA	± 7	± 7
Informed Consent	X								
Medical History	X								
Inclusion/Exclusion Criteria	X	X							
Randomization (IRT)		X							
Vital Signs	X	X	X	X	X	X	X		
Physical Examination including Weight ¶	X	X	X	X	X	X	X		
Height	X								
12-lead ECG	X	X				X			
Clinical Labs ††	X	X	X	X	X	X	X		
PSA ‡‡	X	X	X	X	X	X		X	
Testosterone ‡‡					X ¶¶¶¶			X	
CT/MRI and Bone Scan §§, ¶¶	X §§				X ¶¶¶¶			X	
Chest X-ray or Chest CT/MRI †††	X				X ¶¶¶¶			X	
ECOG Performance Status	X	X	X		X ¶¶¶¶	X	X		
QoL Assessment (QLQ-PR25, EQ-5D-5L, FACT-P, Brief Pain Inventory-Short Form)		X			X ¶¶¶¶	X		X ‡	X ‡
Adverse Events ¶¶¶¶	X	X	X	X	X	X	X	X ¶¶¶¶	
Previous and Concomitant Medications	X	X	X	X	X	X	X		
Study Drug Dispensing		X	X	X	X				
Study Drug Treatment		X	X	X	X				

CT: computed tomography; ECG: electrocardiogram; ECOG: Eastern Cooperative Oncology Group; EQ-5D-5L: EuroQol Group-5 Dimension-5 Level Instrument;

IRT: Interactive Response Technology; MRI: magnetic resonance imaging; NA: not applicable; PSA: prostate-specific antigen;

FACT-P: Functional Assessment of Cancer Therapy-Prostate; QLQ-PR25: Quality of Life Prostate-specific Questionnaire; QoL: quality of life

Before the sponsor's formal determination on study-wide unblinding, open-label enzalutamide will be supplied for free to the subjects in placebo arm who remain on study treatment until confirmed radiographic disease progression and in the judgement of the investigator who is necessary to initiate the next course of therapy till next disease progression based on subject's informed consent. If the study results in a positive outcome and after the sponsor's formal determination on study-wide unblinding via written notice to study sites, open-label enzalutamide will be supplied for free to the subjects in both enzalutamide and placebo arms who remain on study treatment (See [Appendix 12.10]). Subjects who will go to open-label phase will not enter the long-term follow-up.

- CONFIDENTIAL -

[figure not shown]
The alternative approaches which are only permissible in the event of a crisis, is presented in [Section 12.11].

- # All the assessments on Day 1 need to be performed before treatment.
- † Unscheduled visits may be performed at any time during the study whenever necessary to assess for or follow-up on adverse events at the subject's request or if deemed necessary by the investigator. Procedures and assessments are to be performed as clinically indicated.
- ‡ After treatment discontinuation, all subjects MUST undergo long-term follow-up. Long-term follow-up assessments will be composed of post-treatment follow-up and survival follow-up. For those subjects who discontinue study treatment without radiographic disease progression confirmed will undergo post-treatment follow-up (calculated from baseline), include monitoring for survival status, disease progression, new antineoplastic therapies for prostate cancer and symptomatic skeletal events. Subjects will continue to be scanned along with collecting PSA and testosterone every 12 weeks until radiographic progression is confirmed by investigator assessment or the required number of PSA progression events for the final analysis is reached. For those subjects who discontinue study treatment due to confirmed radiographic disease progression will undergo survival follow-up (calculated from date of progression), include monitoring for survival status, new antineoplastic therapies for prostate cancer and symptomatic skeletal events, and the follow-up may be conducted by telephone interview. If seen in clinic, QoL assessment will also be completed until the initiation of new antineoplastic therapy for prostate cancer or the required number of PSA progression events for the final analysis is reached. Additional follow-up contacts may be requested.
- § Or prior to initiation of another investigator agent or new antineoplastic therapy for prostate cancer, whichever occurs first.
- ¶ A brief physical examination is required at each visit, with the exception of the screening visit during which a complete physical examination will be completed.
- †† Laboratory assessments include serum chemistries and hematology.
- ††† For subjects who discontinue study treatment without confirmed radiographic progression, subjects will continue to be collected PSA and testosterone every 12 weeks until radiographic progression is confirmed or the required number of PSA progression events for the final analysis is reached.
- §§ The abdominal-pelvic contrast CT scan or MRI, bone scan, chest x-ray or chest contrast CT must occur within 6 weeks of day 1; otherwise the screening visit assessment must be repeated. Radiographic assessments performed prior to informed consent, as part of the routine care, may be used as the baseline assessment if performed within 6 weeks of day 1 and if digital format images are available for submission to the sponsor.
- ¶¶ The window for all radiological (CT/MRI) assessments is  $\pm$  7 days. For subjects who discontinue study treatment without radiographic progression, subjects will continue to be scanned every 12 weeks until radiographic progression is confirmed or the required number of PSA progression events for the final analysis is reached.
- †††† Chest contrast CT or chest MRI is required at all imaging time points if screening chest x-ray demonstrates metastatic chest disease.
- §§§ Adverse events collection begins after the signing of the informed consent for the double-blind period and will be collected until 30 days after the last dose of study drug (including the double-blind period and open-label phase if applicable), or initiation of a new therapy for prostate cancer, or the subject is determined to be a screen failure, whichever occurs first. During the post treatment follow-up period, only symptomatic skeletal events need to be reported.
- †††† Testosterone, CT/MRI and Bone Scan, Chest X-ray or Chest CT or MRI, QoL Assessment and ECOG Performance Status will only be performed at day 85 and every subsequent 84 days (13 and every subsequent 12 weeks).
- ¶¶¶ The Screening period is 28 days. Re-screening may be allowed once and upon discussion with the medical monitor.

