#### PSA Response $\geq$ 50%, PSA Response $\geq$ 90%:

PSA response  $\geq$  50% is defined as  $\geq$  50% reductions in PSA level from baseline to the lowest post-baseline PSA result as determined by the central laboratory, with a consecutive assessment conducted at least 3 weeks later to confirm the PSA response. The same logic for PSA response  $\geq$  90%. The serum PSA response rate will be summarized at each time point. Waterfall plots of the rate of change from baseline will be constructed. PSA response  $\geq$  50% and  $\geq$  90% will be calculated by treatment group for subjects with PSA values at the baseline assessment and at least 1 post-baseline assessment.

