7.12.3 Visit Windows

Visit windows are allowed for certain visits per the schedule of assessments. Patient data will not be excluded from analyses due to the patient's failure to comply with the visit schedule and unscheduled visits are also assigned analysis visit window based on the visit day.

For summary tables reporting results by visit, analyses of efficacy and safety variables will be performed according to the analysis visit windows described in the following Table 8.

Table 8 Analysis Visit Windows

Visit Day Interval	Scheduled Visit	Analysis Visit*
For double-blind treatment period:		
-28<=Visit Day<1	Week -4 to -1 (Day -28 to -1)	Screening
Up to Day 1	Week 1 (Day 1)	Baseline
Day 2 - Day 43	Week 5 (Day 29)	Week 5
Day 44 - Day 71	Week 9 (Day 57)	Week 9
Day 72 - Day 99	Week 13 (Day 85)	Week 13
For the next visits after week 13 during the double-blind treatment period:		
Week X = Week (i*4+13) (i=1,2,3,...)		
Week X target day = i*4*7 + 85 (i=1,2,3,...)		
Week X (Wk X target day - 13 days ; Wk X target day + 14 days)		
Special case for Testosterone, CT/MRI and Bone Scan, Chest X-ray or Chest CT or MRI, QoL Assessment and ECOG Performance Status:		
Week 13 (Day 85) day interval is Day 72 - Day 127 and for the visits after Week13:		
Week X = Week (i*12+13) (i=1,2,3,...)		
Week X target day = i*12*7 + 85 (i=1,2,3,...)		
Week X (Wk X target day - 41 days ; Wk X target day + 42 days)		
However for the (last) visit during the double-blind treatment period, i.e. the last dose day of study drug is recorded,		
the upper boundary of the analysis visit window is 3 days after the last dose day, e.g.:		
Week X = Week (i*4+13) (i=0,1,2,3,...)		
Week X target day = i*4*7 + 85 (i=0,1,2,3,...)		
Week X (Wk X target day - 13 days ; last dose day + 3 days)		
Special case for Testosterone, CT/MRI and Bone Scan, Chest X-ray or Chest CT or MRI, QoL Assessment and ECOG Performance Status:		
Week 13 (Day 85) day interval is Day 72 - Day 127 and for the visits after Week13:		
Week X = Week (i*12+13) (i=1,2,3,...)		
Week X target day = i*12*7 + 85 (i=1,2,3,...)		
Week X (Wk X target day - 41 days ; last dose day + 3 days)		
(last double-blind dose day + 4 ; last double-blind dose day + 42 if not entering open-label phase) or (last double-blind dose day + 4, up to CRF collected last visit prior to the CRF collected open-label phase day 1 visit)	last double-blind dose day + 30 days	30 Day Safety F-up (after last dose or prior to new therapy)

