For open-label phase: all eCRF collected Open Label visits		

Visit Day Interval	Scheduled Visit	Analysis Visit*
eCRF collected open-label day 1 visit up to open-label dose Day 1, or up to open-label informed consent date if not dosed	Open Label Phase Week 1 (Day 1)	Open Label Phase Baseline
Day 2 - Day 43	Open Label Phase Week 5 (Day 29)	Open Label Phase Week 5
Day 44 - Day 127	Open Label Phase Week 13 (Day 85)	Open Label Phase Week 13

For the next visits after week 13 during the open-label phase:
 
Open Label Phase Week X = Week (i*12+13) (i=1,2,3,...)
 
Open Label Phase Week X target day = i*12*7 + 85 (i=1,2,3,...)
 
Open Label Phase Week X (Wk X target day - 41 days ; Wk X target day + 42 days)
		

However for the (last) visit during the open-label treatment period, i.e. the last dose day of study drug is recorded,
 
the upper boundary of the analysis visit window is 5 days after the last dose day, e.g.:
 
Open Label Phase Week X = Week (i*12+13) (i=0,1,2,3,...)
 
Open Label Phase Week X target day = i*12*7 + 85 (i=0,1,2,3,...)
 
Open Label Phase Week X (Wk X target day - 41 days ; last dose day + 5 days)
		
(last open-label dose day + 6, last assessment)	last open-label dose day + 30 days	Open Label Phase 30 Day Safety F-up (after last dose or prior to new therapy)

For long-term follow-up visits conducted after double-blind treatment period or open-label phase:
 
Patients who end treatment before the data analysis cut-off date and have long-term (LT) follow-up visits,
 
have visits every 12 weeks after last dose day:
 
LT F-up j = j*12 weeks visit after last dose day (j=1,2,3,...)
 
LT F-up j target day = j*12*7 + last dose day (j=1,2,3,...)
 
LT F-up j (j*12*7 + last dose day - 41 ; j*12*7 + last dose day + 42)
		

F-up: follow-up; WK: Week

*At OL1 Visit (open-label day 1), the following assessments (ECG; vital signs; physical examination; clinical labs; ECOG) do not need to be repeated if they were completed within 7 days in Safety Follow-up Visit during double blind treatment period, and the corresponding data captured in Safety Follow-up Visit could be captured repeatedly in OL1 CRF forms, thus those assessments will serve the analysis needs for both double blind treatment period and open-label phase where applicable. And “open-label” will be reflected in the open-label phase visits’ label as applicable, e.g. OLP Baseline, Open Label Week X, etc..

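### SAP Table 8 windows post-treatment assessments from last dose although the schedule counts them from baseline, so descriptive by-visit efficacy tables file off-drug results under the wrong time

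*Protocol*

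**What the plan says.** **Schedule.** In the long-term follow-up footnote to Protocol Table 1, patients who stop without confirmed radiographic progression "will undergo post-treatment follow-up (calculated from baseline"). The same footnote adds: "Subjects will continue to be scanned along with collecting PSA and testosterone every 12 weeks". QoL is completed if the patient is seen in clinic. The matching footnote in the SAP's schedule (SAP section 2) also counts from baseline. Patients who stop because of confirmed radiographic progression "will undergo survival follow-up (calculated from date of progression"), with no scheduled PSA or scans.

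**Analysis windows.** SAP 7.12.3, Table 8, states that patients with long-term follow-up "have visits every 12 weeks after last dose day" and sets "LT F-up j target day = j*12*7 + last dose day (j=1,2,3"). For the last on-treatment visit, "the upper boundary of the analysis visit window is 3 days after the last dose day". Days 4 to 42 after last dose belong to the 30-day safety follow-up.

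**Where the windows apply.** SAP 7.12.3 applies Table 8 to all summary tables by visit, for efficacy as well as safety. That covers:
- PSA values (SAP 7.4.1);
- PSA response at each visit (SAP 7.4.2.4; Protocol 7.4.2: "The serum PSA response rate will be summarized at each time point");
- time-point tumour response (SAP 7.4.2.7);
- the QoL scales (SAP 7.4.3.1).

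**The concern.** The SAP windows a visit grid that the schedule does not use, and so contradicts both the protocol and its own footnote. An off-drug patient seen exactly when the protocol asks, at Week 25, 37 or 49, will generally not appear under that week.

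Three things are at stake in the by-visit tables:
- **Week X rows.** They are presented on the ITT population but consist largely of patients still taking drug. That is selection after randomisation, it can differ by arm, and the tables do not label it.
- **LT F-up rows.** They group patients by time since stopping, so one row holds assessments from quite different times since randomisation.
- **Competition within a window.** PSA is also taken at the 30-day safety visit. A grid PSA that falls in the safety window can lose to it, because only the observation closest to the target day is tabulated.

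**Working it through.** **Inputs.** Grid visits fall on Day 85 + 84i (Protocol Table 1). Window formulas are those of SAP Table 8.

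**1. The SAP's own windows reproduce.** For 4-weekly assessments, Week 13 is 85 − 13 = Day 72 to 85 + 14 = Day 99. For scans, the Week 13 upper limit is 85 + 42 = Day 127, and Week 25 is 169 − 41 = Day 128 to 169 + 42 = Day 211.

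**2. Labels by days since last dose.**
- Up to +3: Week X
- +4 to +42: Safety F-up
- 84 − 41 = +43 to 84 + 42 = +126: LT F-up 1
- 168 − 41 = +127 to 168 + 42 = +210: LT F-up 2
- 252 − 41 = +211 to 252 + 42 = +294: LT F-up 3

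These join without gaps. By this rule, a visit more than 3 days after last dose has no Week X label.

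**3. Protocol-scheduled visits under Table 8.**

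| Last dose | Grid visit (study week) | Days since last dose | Label |
|---|---|---|---|
| Day 126 | Day 169 (Week 25) | 43 | LT F-up 1 |
| Day 130 | Day 169 (Week 25) | 39 | Safety F-up |
| Day 100 | Days 169, 253, 337 (Weeks 25, 37, 49) | 69, 153, 237 | LT F-up 1, 2, 3 |
| Day 150 | Days 169, 253, 337 (Weeks 25, 37, 49) | 19, 103, 187 | Safety F-up, LT F-up 1, LT F-up 2 |
| Day 300 | Days 337, 421 (Weeks 49, 61) | 37, 121 | Safety F-up, LT F-up 1 |

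In these few cases LT F-up 1 already holds Weeks 25, 37 and 61. Over stopping days 85 to 756 it holds Weeks 25 to 121.

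**4. Share of first off-drug grid visits.** Assume the stopping day is evenly spread over the 84-day cycle, so the next grid visit falls 1 to 84 days later:
- Week X: 3/84 = 3.6%
- Safety F-up: 39/84 = 46.4%
- LT F-up 1: 42/84 = 50.0%

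**5. Competition in the safety window.** For a last dose on Day 150 the safety target is Day 180. The grid PSA on Day 169 is 11 days from it. A safety PSA inside its ±7-day window is at most 7 days away. If both samples are taken, the grid PSA drops out of the by-visit table.

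**6. One exception inside Table 8.** The last-visit block prints the Week 13 interval for scans, testosterone and QoL as Day 72 to 127 without the last-dose cap. A Day 85 scan after a last dose on Day 60 then fits both Week 13 and Safety F-up (85 − 60 = +25). The SAP does not say which label applies.

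**7. Number of patients.** The documents give none. If 5% to 30% had stopped without radiographic progression or new therapy (an assumption), that would be 6 to 36 of 120 and 3 to 18 of 60 patients missing from a week column.

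**The case against.** **No test or endpoint comparison uses these labels.** This stands in full. SAP 7.12 bases time-to-event endpoints on actual dates, so TTPP and rPFS are untouched. The compared PSA response is the maximal decline at any time, the PSA undetectable rate uses any post-baseline value, and ORR uses best response. SAP 7.1 makes all non-primary p-values descriptive. A reader might infer that the efficacy comparisons are biased; the documents do not support that.

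**Results are relabelled rather than removed, and the restriction is not absolute.** This largely stands. A reader might infer that every weekly table contains only patients on drug. That goes too far: Week X admits 3 days after last dose, the Week 13 interval for scans, testosterone and QoL is printed uncapped, and off-drug results still appear under follow-up labels. The exception is a grid value that loses its place to the safety visit.

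**Much of the selection comes from the design, not from Table 8.** This also stands. Patients who stop for confirmed radiographic progression have no further scheduled PSA or scans. PSA response uses only samples before new antineoplastic therapy. Open-label entrants do not enter the long-term follow-up, and PSA is not assessed in that phase. The PSA undetectable rate is on-treatment by definition (Protocol 7.4.2, SAP 7.4.2.6) and is not an example of the problem.

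**Separating on-drug from off-drug summaries is a legitimate descriptive choice.** It is, if stated. Here the tables are declared ITT, and SAP 7.4 defines the double-blind period by blinding, not by dosing. SAP 7.12.3 also assigns unscheduled visits by visit day, so an off-schedule on-drug visit receives a week label while a scheduled off-drug visit does not. Nor does this choice explain a follow-up anchor that contradicts the schedule.

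**Conclusion.** The contradiction is certain: the protocol and the SAP's schedule footnote count from baseline, and SAP Table 8 counts from last dose. The mislabelling follows from Table 8's arithmetic and needs no assumption. The 46.4%, 50.0% and 3.6% split assumes evenly spread stopping days and describes labels, not bias.

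The effect is confined to descriptive by-visit summaries of PSA, PSA response, time-point tumour response, testosterone and QoL. A reader might want a figure for how far the weekly response rates, or the difference between arms, are distorted. The documents support none: they give neither the number of patients off drug and still followed nor their response rates.

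The SAP should still be corrected, because the stated rule contradicts the schedule it is meant to window.

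**What to change.** Revise SAP 7.12.3 as follows:
- For patients who stopped without confirmed radiographic progression, assign post-treatment PSA (up to new antineoplastic therapy), testosterone, imaging and QoL to 12-weekly Week X windows by study day from baseline. Apply no last-dose + 3 cap, and stop at open-label entry or cut-off. Re-anchoring the LT F-up rows alone would not be enough, because the cap would still exclude off-drug data from the week rows.
- Keep last-dose windows for safety variables and the 30-day visit.
- State which rule wins where windows overlap, including the uncapped Week 13 interval and a grid assessment that falls in the safety window.
- Show on-drug and off-drug counts in each week row.
- Leave the PSA undetectable rate on-treatment, as defined.

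The cost is SAP wording and window programming; SAP section 1 allows revision before hard lock. Two limits remain. Off-drug PSA exists only every 12 weeks, so the intermediate 4-weekly rows stay on-drug and should be labelled so. Week rows will also still omit patients who left PSA or scan follow-up after radiographic progression and, for PSA, after new therapy.
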